Introduction and rationale	Lung cancer is the most common cause of cancer-related death among all human cancers, with two million new cases diagnosed worldwide in 2018 (Ferley et al, 2019). Non–small-cell lung cancer (NSCLC) accounts for more than 85% of lung cancers and the most common histology in this group is adenocarcinoma (Siegel et al, 2015). About 20% of adenocarcinomas have genomic changes in driver genes, namely, activating point mutations in EGFR or BRAF and gene fusions involving the ALK or ROS1 genes, which are predictive biomarkers for biological therapies having as targets the abnormal proteins coded by those somatic genetic changes (Hanna et al, 2017). Although such targeted therapies helped to significantly improve the prognosis of these molecular subtypes of NSCLC, multiple resistance mechanisms have been described after first-line targeted treatment, which may be highly relevant for the informed choice of second-line therapy. In NSCLCs with EGFR-sensitizing mutations, the most frequent mechanism of resistance to first-line anti-EGFR therapy is the emergence of the T790M EGFR mutation, which in turn is predictive of response to osimertinib (Planchard et al, 2018). Progression of ALK-positive NSCLC under treatment with first-line anti-ALK therapy is often associated with secondary point mutations in ALK, which may predict which second-line anti-ALK therapy is likely to be more effective. However, contrary to what is the case for EGFR-positive NSCLC, identification of the mechanism of resistance is recommended but not mandatory in ALK-positive NSCLC patients (Lindeman et al, 2018). The expanding number of mechanisms of resistance to biological therapies and the availability of several lines of treatment in NSCLC patients is creating the necessity for real-time tumor genotyping, yet tissue biopsies are	

difficult to perform serially and often yield inadequate DNA for next-generation sequencing (NGS). For instance, the guidelines include the option to start to test for the T790M EGFR mutation first in circulating tumor DNA (ctDNA) and to rebiopsy only if that mutation is not detected in ctDNA (Planchard et al, 2018). ctDNA mutation testing with NGS potentially facilitates the study of genotypically heterogeneous tumors and allows identification of multiple resistance mechanisms in NSCLC patients (Chabon et al, 2016), but the clinical relevance of this strategy requires additional studies.

For ctDNA testing in patients progressing on first-line anti-EGFR therapy, we currently use the CE-IVD cobas® EGFR Mutation Test v2 for the qualitative detection and identification of mutations in EGFR exons 18, 19, 20, and 21, including the T790M mutation. In this setting and with this method, we detect a EGFR mutation in ctDNA in 66.6% of the patients, which is in line with a large metaanalysis (Li et al, 2014) showing 65% sensitivity (95% confidence interval: 61-68%). In this pilot study, we intend to evaluate the feasibility of using the AVENIO ctDNA Expanded Kit, a NGS liquid biopsy tumor profiling assay for identifying genomic aberrations derived from solid tumors, in NSCLC patients progressing after first-line targeted treatment. This investigational test analyses 77 genes, including those currently in the NCCN Guidelines and emerging biomarkers relevant to clinical research.

Study objective(s)

The primary objective of this pilot study is to evaluate the overall sensitivity of the AVENIO ctDNA Expanded Kit to detect the primary molecular change in NSCLC patients progressing after first-line targeted treatment with an approved targeted therapy for those molecular subtypes of NSCLC.

The secondary objectives are:

- To describe the pattern of resistance mechanisms in patients with EGFR, BRAF, ALK, or ROS1-positive NSCLC who progressed after first-line treatment.
- To evaluate the rate of potential access to other approved or off-label targeted therapies.
- To evaluate the potential impact of this strategy to reduce the rate of rebiopsies in these patients, as compared with historical data from the year before.

2. Investigational material

Investigational material and comparator product(s)

The investigational assay to be used in this study is the AVENIO ctDNA Expanded Kit on a NextSeq 550 sequencer and the Oncology Analysis Server equipment, AVENIO software 2.0 and a report will be issued using NAVIFY Mutation Profiler software.

The comparator product in this study with be the routine use of the CE-IVD cobas® EGFR Mutation Test v2, which will be used in parallel in ctDNA from patients with EGFR-positive NSCLC in progression. We will use the 95% confidence interval values (61-68%; mean 65%) reported in the metaanalysis of Li et al (2014) as the cut-off points for assessing superiority (>68%), inferiority (<61%) or non-inferiority (61-68%).

3. Study population

Recruitment, enrollment

100 patients will be recruited from all major cancer hospitals in Portugal over a planned recruitment period of 12 months.

period, and	
sample size	
Inclusion criteria	Adult patients with EGFR, BRAF, ALK, or ROS1-positive NSCLC who progressed after first-line treatment with an approved targeted therapy for those molecular subtypes of NSCLC who have not yet initiated second-line therapy.
Exclusion criteria	 Patients without EGFR, BRAF, ALK, or ROS1-positive NSCLC. Patients with EGFR, BRAF, ALK, or ROS1-positive NSCLC still responding to first-line treatment. Patients with EGFR, BRAF, ALK, or ROS1-positive NSCLC who progressed after first-line treatment and have initiated second-line therapy. Patients under the age of 18.
4. Study design and study procedure	
Study design	This will be an exploratory, multicenter, national, prospective, observational study.
Study procedure	Patients will be enrolled at the time of the Medical Oncology appointment in which progression after first-line targeted treatment is established. ctDNA testing for patients with EGFR-positive NSCLC will be ordered as usual and the surplus sample will be used for NGS. In the institutions where ctDNA EGFR testing is not routinely ordered and in patients with BRAF, ALK, or ROS1-positive NSCLC, ctDNA testing by NGS will be requested at the time of the first peripheral blood sample taken as part of his/her regular follow up. Peripheral blood samples for ctDNA testing will be collected in specific tubes for that purpose (to preserve ctDNA quality and avoid contamination with cellular DNA) and will be sent to the Department of Genetics of IPO-Porto as soon as possible (at room temperature). Samples from IPO Porto will be processed within 4 hours and samples from other hospitals will be sent by express mail and processed within 48 hours. Clinical decisions in patients with EGFR-positive NSCLC who progressed after first-line targeted treatment with an approved targeted therapy will be based on the ctDNA testing with the CE-IVD cobas® EGFR Mutation Test v2 whenever that test is already routinely used in any particular participating institution. The investigational assay AVENIO ctDNA Expanded Kit will be used in parallel in the surplus ctDNA sample and will be validated for its performance to detect EGFR mutations as compared with the current gold standard. In light of the potential higher sensitivity of the NGS test (limit of detection ≤1%) compared to the routine testing (limit of detection ≤5%) for EGFR mutations, this information will be provided to the treating clinician. Furthermore, whenever ctDNA testing is currently not routinely requested in EGFR, BRAF, ALK, or ROS1-positive NSCLC patients progressing after first-line treatment, the research information will be provided to the treating clinician. Given the recommended sample input for each test, two peripheral blood sample draws need to be collected for EGFR

Subjects have the right to withdraw from the study at any time for any reason. If lost to follow-up, the assigned study staff will try to contact the subject by telephone followed by registered mail to establish and document as completely as possible the reason for the withdrawal. Subjects will be informed of circumstances under which their participation may be terminated by the responsible investigator without the subject's consent. The investigator may withdraw subjects from the study in the event of intercurrent illness, adverse events, lack of compliance with the study and/or study procedures (e.g., study visits), or any reason where it is felt that it is in the best interest of the subject to be terminated from the study. Any administrative or other reasons for withdrawal will be documented and explained to the subject. If the reason for removal of a subject from the study is an Adverse Event, the principal specific event will be recorded in the medical record.

5. Statistics

Primary and secondary endpoint(s)

To evaluate the overall sensitivity of the AVENIO ctDNA Expanded Kit to detect the primary molecular change in NSCLC patients progressing after first-line targeted treatment with an approved targeted therapy for those molecular subtypes of NSCLC.

The secondary endpoints are:

- Number of resistance mechanisms in patients with EGFR, BRAF, ALK, or ROS1-positive NSCLC who progressed after first-line treatment.
- The rate of potential access to other approved or off-label targeted therapies.
- The rate of rebiopsies in these patients, as compared with historical data from the year before.

Statistical methods

Not applicable as it is a pilot study.

Sample size, level of significance, and power

Not applicable as it is a pilot study. We will use the 95% confidence interval values (61-68%; mean 65%) reported in the metaanalysis of Li et al (2014) as the cut-off points for assessing superiority (>68%), inferiority (<61%) or non-inferiority (61-68%). If statistical power falls short after first 100 patients, cohort could be extended.

6. Safety assessment

Not applicable as it is an observational study. Treatment is not part of the protocol but done at physicians' decision, so safety assessment is not applicable.

7. Compliance Statements

General requirements: The study will be conducted in compliance to this study protocol, the current version of the Declaration of Helsinki, ICH GCP, and applicable local legal and regulatory requirements.

Submission of study documents: Before study start, the study protocol, and subject information / informed consent and any other study-related document as required by applicable laws and regulations will be submitted to the Ethics Committee and regulatory authorities for written approval.

Any protocol amendments or new or amended information that requires ethical consideration will be submitted for written approval, too. In addition, a study report (interim and /or full report) will be submitted to regulatory authorities in line with applicable timelines.

Subject information and informed consent: Subjects/legal representatives will be informed orally and in writing about the objectives of the study, study procedures, potential risks, and about the fact that to some extent data will be accessible for third parties (see below) for the purpose of controlling the study conduct - provided that data confidentiality is ensured at any time.

Before any study-related activities are initiated, the subjects / legal representatives will have to sign the written informed consent. The participation in the study is entirely voluntary. The subjects have the right to withdraw their willingness to participate in the study at any time without affecting their future medical care in any way.

Clinical study results and publication: The results of the clinical study will be documented in a clinical study report and if possible, will be published (e.g. in a journal or presented in a scientific meeting).

8. Data confidentiality and protection

Data confidentiality and data protection

Auditors, Ethics Committee, and the regulatory authorities will be granted direct access to the subject's medical records to the extent permitted by the applicable law and regulation for verification of clinical study procedures, and/or data control, ensuring subject data confidentiality. The subject's file and the source data will be archived in line with national and international legal requirements. The key that allows patient identification will be eliminated 5 years after the end of the study.

9. Quality controls and assurance

Quality controls and quality assurance

The gold standard test is the CE-IVD cobas® EGFR Mutation Test v2, which will be used according to the manufacturer's instructions. The Department of Genetics is regularly enrolled in external quality assessment using this test.

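### The superiority and inferiority rule sets AVENIO against a historical interval and leaves out the concurrent cobas results, so the verdict depends on the cohort as well as the assay

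*Protocol*

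**What the plan says.** **Comparator.** Section 2 (Investigational material and comparator product(s)) states: "The comparator product in this study with be the routine use of the CE-IVD cobas® EGFR Mutation Test v2". On when and in whom this happens, the same sentence adds "which will be used in parallel in ctDNA from patients with EGFR-positive NSCLC in progression".

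**Decision rule.** The next sentence of section 2 turns to an outside source: "We will use the 95% confidence interval values (61-68%; mean 65%) reported in the metaanalysis", to serve "as the cut-off points for assessing superiority (>68%), inferiority (<61%) or non-inferiority (61-68" (the last band closes at 68%). Section 5 repeats the rule under sample size, level of significance and power, and otherwise declares statistical methods and sample size not applicable because this is a pilot.

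**Quantity judged.** The primary objective is to "evaluate the overall sensitivity of the AVENIO ctDNA Expanded Kit to detect the primary molecular change in NSCLC patients", that is, across EGFR, BRAF, ALK and ROS1. Section 3 plans 100 patients over all four subtypes.

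**Concurrent cobas data.** Section 4 has AVENIO run on surplus sample alongside cobas and validated for EGFR against it. Section 9 likewise says that AVENIO's EGFR performance will be measured against cobas. Both sections call cobas the gold standard, and neither gives a quantity to estimate or a rule. Section 4 bases clinical decisions on cobas "whenever that test is already routinely used in any particular participating institution". EGFR-positive patients at other institutions, and all BRAF, ALK and ROS1 patients, are described as having NGS.

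**Site experience.** The introduction reports: "In this setting and with this method, we detect a EGFR mutation in ctDNA in 66.6% of the patients".

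**The concern.** The share of patients whose driver is found in plasma depends on two things: the assay, and how much tumour DNA those patients shed. A fixed historical cut-off cannot tell them apart. A high-shedding cohort lifts any assay above 68%, and a low-shedding one pulls any assay below 61%. The word superior then says little about AVENIO relative to cobas, although cobas is the named comparator and its results on the same patients will be to hand.

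An assay no better than routine testing could be reported as superior, or an equivalent one as inferior. The protocol commits to these labels in two places, so this is a rule fixed on a poor basis and not a detail left for a later analysis plan.

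**Working it through.** The protocol gives no test, significance level, effect size or power, so there is no derived figure to reproduce. The check is how the stated rule behaves.

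**Inputs from the protocol.** n = 100 (section 3); superior above 68%, non-inferior 61-68%, inferior below 61% (sections 2 and 5); the site's cobas detection rate of 66.6% (introduction).

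**Assumptions.** AVENIO and cobas have the same true sensitivity p in the enrolled cohort, with p varied from 55% to 75%. All 100 patients count towards the rule.

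**Step 1: the rule when the assays are equal.** With X detections out of 100, X ~ Binomial(100, p). An observed rate above 68% means X ≥ 69, and below 61% means X ≤ 60. So P(superior) = P(X ≥ 69), P(inferior) = P(X ≤ 60), and the remainder is non-inferior.

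| Common sensitivity p | Superior | Non-inferior | Inferior |
|---|---|---|---|
| 55% | 0.3% | 13% | 87% |
| 60% | 4% | 42% | 54% |
| 65% | 23% | 59% | 17% |
| 66.6% | 35% | 55% | 10% |
| 70% | 63% | 35% | 2% |
| 75% | 93% | 7% | 0.1% |

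The true difference between assays is zero in every row. The verdict moves from mostly inferior to almost always superior on cohort sensitivity alone. With fewer patients the pattern is the same: at 66.6%, P(superior) is 39% with n = 80 and 45% with n = 60.

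**Step 2: sampling error against the width of the bands.** An observed 65/100 has an exact (Clopper-Pearson) 95% interval of 54.8% to 74.3%, about 19.5 points wide. The whole non-inferior band is 68 − 61 = 7 points. A point estimate cannot be placed reliably in one band even without a shift in case mix.

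**Step 3: what pairing changes.** Let b be the proportion positive on AVENIO only and c the proportion positive on cobas only, both scored against the known driver. The paired difference is b − c. If the assays are equal then b = c, whatever the cohort's sensitivity. An exact two-sided 5% McNemar test then favours AVENIO wrongly at most 2.5% of the time.

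**Step 4: what pairing does not promise.** Assume cobas 65% and AVENIO 75% (b − c = 10 points), with c from 5% down to 1%. None of these values is in the protocol, nor is the number of pairs. The last column tests AVENIO alone against 65% treated as exactly known, one-sided 2.5%.

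| Patients | Exact McNemar power | One-sample power against 65% |
|---|---|---|
| 60 | 31-49% | 33% |
| 80 | 44-70% | 46% |
| 100 | 54-83% | 55% |

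At c = 5% the paired test is slightly the weaker. The same holds at n = 70 with b = 15% and c = 5%: 37% paired against 40% one-sample. With only 40 pairs, b = 12% and c = 2%, paired power is 20%.

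**The case against.** The strongest reply is that the head-to-head comparison has not been dropped. Sections 4 and 9 both commit to assessing AVENIO's EGFR performance against cobas, and the statistic for it may be in an analysis plan that is not shown. This stands: it would be wrong to infer that the historical figure replaces the concurrent comparison, or that the study can say nothing about AVENIO relative to cobas. But the protocol does fix the verdict, and fixes it without those data. Also, if cobas is taken as the truth, as the gold-standard label suggests, a true mutation found only by AVENIO counts as an error. Superiority could not be shown that way.

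A reader might also infer that sections 2 and 4 contradict each other on who gets cobas. The text does not support this firmly: section 2 defines the comparator as routine use of the test, which fits section 4's restriction to institutions where it is routine. Nor does the protocol propose comparing AVENIO in all EGFR patients with cobas in a subset.

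The benchmark is not arbitrary, since the site's 66.6% lies close to the meta-analysis mean of 65%. This makes a large shift less likely but does not exclude one, and at exactly 66.6% the rule still calls equal assays superior 35% of the time.

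Finally, cobas tests EGFR only, so pairing cannot serve a primary quantity that spans four drivers, and an exploratory pilot may reasonably use an outside reference. That supports keeping the interval as context. It does not support drawing superiority or inferiority labels from it, particularly as it is cited for EGFR detection and applied to an overall figure.

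**Conclusion.** The concern holds in this form: the only superiority, non-inferiority and inferiority rule makes no use of the concurrent cobas results, and so confounds assay performance with case mix. For two equally sensitive assays and n = 100, the chance of a superior verdict runs from 4% to 93%, and of an inferior verdict from 54% to 0.1%, as common sensitivity goes from 60% to 75%. At the site's own cobas rate the figures are 35% and 10%.

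These probabilities rest on the stated cut-offs and n = 100, on equal sensitivity, and on the assumed range of cohort sensitivity. A reader might go further and infer that pairing brings a clear gain in power. The documents do not support that: they give neither the number of paired patients nor any discordance rate, and under plausible discordance the paired test can do slightly worse than a one-sample test against a fixed 65%. The case for pairing is freedom from confounding. The point should be acted on, but it does not invalidate the study's descriptive aims.

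**What to change.** In sections 2 and 5, separate the comparative statement from the overall estimate.

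- **EGFR-positive patients with both results.** Score AVENIO and cobas each against the known primary EGFR mutation, not AVENIO against cobas as truth. Report both detection rates, the discordant counts, and the paired difference with its 95% confidence interval and exact McNemar test. Base any superiority statement against cobas on that interval.
- **Non-inferiority.** Claim it only against a margin on the paired difference, set and justified before the data are seen. The protocol has no such margin now.
- **All four drivers.** Report overall AVENIO sensitivity descriptively with its exact 95% confidence interval.
- **The 61-68% interval.** Keep it as context, without verdict labels.
- **Size of the paired set.** State the expected number of EGFR-positive patients with a routine cobas result.

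**Cost.** No new assay or patient is needed, because both results already arise where cobas is routine. The work is a change of wording and the choice of a margin. The price is scope: the comparative verdict covers only EGFR-positive patients at hospitals that routinely use cobas, its power is unknown and may be low, and BRAF, ALK and ROS1 patients have no comparative verdict.

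### In EGFR-positive patients at hospitals that routinely use cobas, the observed rebiopsy rate mixes assay performance with how far clinicians acted on the NGS result, so it cannot by itself measure the potential impact named in the objective.

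*Protocol*

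**What the plan says.** Section 4 (Study procedure) makes two statements about EGFR-positive patients at institutions where cobas is routine. Clinical decisions "will be based on the ctDNA testing with the CE-IVD cobas® EGFR Mutation Test v2 whenever that test is already routinely used". AVENIO is run in parallel on surplus sample and, because its limit of detection may be lower (≤1% against ≤5%), "this information will be provided to the treating clinician". Where ctDNA testing is not routinely requested, "the research information will be provided to the treating clinician", with no competing statement about cobas.

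The secondary objective (section 1) is "To evaluate the potential impact of this strategy to reduce the rate of rebiopsies in these patients"; the same sentence goes on to name a comparison with the preceding year. The matching endpoint (section 5) is "The rate of rebiopsies in these patients, as compared with historical data from the year before". The word potential is in the objective but not in this endpoint. The endpoint on access to other therapies, by contrast, keeps it in both places.

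The introduction explains how a ctDNA result can bear on rebiopsy: it cites a guideline option to test for T790M in ctDNA first and "to rebiopsy only if that mutation is not detected in ctDNA".

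**The concern.** The patient in whom NGS could spare a rebiopsy is one whose cobas result leaves the question open and whose AVENIO result would settle it. At cobas-routine institutions, that is the patient for whom the visible text gives no rule. It also does not say whether the AVENIO report arrives before or after the rebiopsy decision.

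If the clinician follows cobas, or the AVENIO report comes too late, NGS cannot change whether a rebiopsy is done, however good the assay is. If the clinician acts on AVENIO, it can. The observed rate in this stratum is therefore a blend of the two, and the protocol does not say that the blending proportion will be recorded. A small or absent fall could mean that the assay adds little or that its results were not acted on, and the endpoint cannot tell these apart. An ideal control year would not cure this, so the point is separate from any weakness of the historical comparison.

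**Working it through.** The protocol states no rebiopsy rate, historical rate or effect size, so there is no planned figure to reproduce. The dependence can still be written down.

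**Notation**
- pC: rebiopsy rate if cobas alone is followed.
- pN: rebiopsy rate if the NGS result is followed.
- a: share of clinicians in the cobas-routine EGFR stratum who act on NGS.
- s: share of the whole cohort in that stratum.

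**Formulas**
- Reduction due to NGS in the stratum: pC − [a·pN + (1 − a)·pC] = a·(pC − pN).
- Observed rate in the whole cohort: s·[a·pN + (1 − a)·pC] + (1 − s)·pN.

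The first formula carries the point. The product a·(pC − pN) is all that the observed rate can reveal, and pC − pN cannot be recovered without knowing a.

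**Inputs**
- pC = 1 − 0.666 = 0.334. Section 1 reports that cobas detects an EGFR mutation in 66.6% of patients. The complement is non-detection of any EGFR mutation. It is neither a T790M rate nor a rebiopsy rate, and it stands in for one here by assumption.
- pN, a and s are assumed over ranges. For simplicity the same pC and pN are used for all patients.

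**Reduction within the cobas-routine stratum (percentage points)**

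| pN | a = 0 | a = 0.5 | a = 1 |
|---|---|---|---|
| 15% | 0 | 9.2 | 18.4 |
| 20% | 0 | 6.7 | 13.4 |
| 25% | 0 | 4.2 | 8.4 |
| 30% | 0 | 1.7 | 3.4 |

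For example, with pN = 20% and a = 0.5: 0.5 × (33.4 − 20) = 6.7.

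**Observed rate in the whole cohort, pN = 20%**

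| s | a = 0 | a = 0.5 | a = 1 |
|---|---|---|---|
| 0.3 | 24.0% | 22.0% | 20.0% |
| 0.9 | 32.1% | 26.0% | 20.0% |

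The ambiguity is 4.0 points wide if 30% of patients are in this stratum and 12.1 points if 90% are. The protocol does not give the share.

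**What a within-patient count would show instead.** Assume 50 EGFR-positive patients at cobas-routine institutions, 60% without T790M by cobas, and a sufficient AVENIO finding in 10% to 30% of those. Then 50 × 0.60 = 30 patients are candidates, and 3 to 9 rebiopsies are potentially avoidable (3/50 = 6 points, 9/50 = 18 points). One bound follows from the document. T790M is itself an EGFR mutation, so at the study centre at least 33.4% are T790M-negative by cobas. At that minimum the range is 0.334 × 0.10 = 3.3 to 0.334 × 0.30 = 10.0 points. Unlike the observed rate, this count does not depend on a.

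**The case against.** Several objections have force.

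- **The two statements need not conflict.** Cobas can be the standard, with NGS as further information that the physician may use. The study is observational and leaves treatment to the physician. This reading is natural, and a flat contradiction is not shown. But under it a lies somewhere between 0 and 1 and is not stated to be recorded, so the difficulty remains.
- **The objective itself names the comparison with the preceding year.** That is correct, and the observed comparison is a legitimate part of the plan. It still does not deliver the potential impact in this stratum.
- **The stratum is only part of the cohort.** This stands. Where ctDNA testing is not routine, including BRAF, ALK and ROS1 patients in that position, the NGS result is released without a competing cobas statement. The observed rate there does reflect NGS-informed care.
- **The T790M-first rule is a guideline option cited in the rationale, not the study's rebiopsy rule.** This stands, and so the definition of a sufficient finding has to be fixed in advance.
- **An SAP could define a within-patient measure from the parallel results.** It could. It could not supply the reason for a rebiopsy, or the order of results and decision, if these are not collected.
- **The available text of Study procedure breaks off mid-sentence.** A later rule on discordant results cannot be excluded.

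A reader might infer that the rebiopsy rate shows only which rule each site followed and nothing about NGS, or that a null result would prove that the design blocked the effect. The documents do not support either. The rate is a mixture, the effect is blocked only if cobas alone is followed, and other groups are unaffected.

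**Conclusion.** The point holds for EGFR-positive patients at cobas-routine institutions and not for the whole cohort. In that stratum the observed rebiopsy rate cannot by itself measure potential impact, because it confounds what the assay could spare with how far its results were used. The direction is certain: the visible effect is the full effect multiplied by a fraction between zero and one. The size is not known. The 0 to 18.4 points above rest on an assumed cobas-rule rebiopsy rate of 33.4% and assumed NGS-rule rates of 15% to 30%; the 3 to 9 avoidable rebiopsies in 50 rest wholly on assumptions.

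This affects one secondary endpoint of an exploratory pilot. The primary sensitivity objective is untouched. The point is worth acting on because the parallel results already allow a better measure at small cost.

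**What to change.** 1. Reconcile the two Study procedure statements with each other and with the rebiopsy objective, so that the handling of discordant results is stated. Which test governs care is not for this review to say. Identical handling at every site is not needed for the statistics, nor is holding back AVENIO reports.
2. Add a within-patient measure in patients with both results: among those without a cobas ctDNA finding that would make a rebiopsy unnecessary, the proportion in whom AVENIO reports one; and the reverse, among those with such a cobas finding, the proportion in whom AVENIO does not. The sponsor should fix the definition of such a finding before results are seen.
3. Record the dates of both results and the reason for each rebiopsy.
4. Keep the observed rate against the previous year as descriptive, reported separately for cobas-routine EGFR, non-routine EGFR, and BRAF/ALK/ROS1 patients.

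The cost is a few extra data items and some endpoint wording. The added measure describes potential rather than performed rebiopsies, which is what the objective asks for, and the observed rate remains beside it.

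### The superior / non-inferior / inferior verdict sets a point estimate from about 100 patients against the confidence limits of a pooled mean, so an assay equal to the benchmark is mislabelled about 40% of the time

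*Protocol*

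**What the plan says.** The primary objective and endpoint (study objectives; Section 5, Statistics) is a single proportion: "To evaluate the overall sensitivity of the AVENIO ctDNA Expanded Kit to detect the primary molecular change". The introduction cites a meta-analysis of EGFR testing in blood "showing 65% sensitivity (95% confidence interval: 61-68" per cent). It gives the centre's own rate with the routine test as follows: "we detect a EGFR mutation in ctDNA in 66.6% of the patients".

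The decision rule appears in Section 2 (comparator product) and again in Section 5 (sample size, level of significance, and power). Its source is given as "We will use the 95% confidence interval values (61-68%; mean 65%) reported in the metaanalysis", and these values serve "as the cut-off points for assessing superiority (>68%), inferiority (<61%) or non-inferiority (61-68" per cent).

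In Section 5, the entry on statistical methods and the opening of the entry on sample size, significance level and power are the same: "Not applicable as it is a pilot study". Section 3 sets the size: "100 patients will be recruited from all major cancer hospitals in Portugal over a planned recruitment period of 12 months". Section 5 adds: "If statistical power falls short after first 100 patients, cohort could be extended".

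**The concern.** Superiority, non-inferiority and inferiority are inferential statements. Each needs the study's own uncertainty to be set against a justified bound. Here the three labels partition the scale at 61% and 68%, and no interval, test or error rate is attached to the study's estimate.

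The cut-offs are also of the wrong kind. The limits 61-68% describe how precisely a pooled mean is known. They are not a margin of acceptable loss, and they are not the range in which a 100-patient sample would fall if the new assay performed like the benchmark.

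The verdict attaches to the primary objective, and Section 7 foresees a report to regulatory authorities and publication. A headline of superior or inferior could therefore arise by chance from an assay that the data cannot tell apart from the benchmark.

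**Working it through.** The protocol gives no alpha, power or sample-size derivation, so it has no figure of its own to reproduce.

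**Inputs.** n = 100 (Section 3). Cut-offs 61% and 68%, benchmark 65% (Sections 2 and 5). Routine-test rate at the centre 66.6% (introduction). Assumption: all 100 patients are evaluable.

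**Does the rule act on a point estimate?** The protocol does not say so; it is an inference. The bands are exhaustive, with no indeterminate zone. At 65/100 the exact (Clopper-Pearson) 95% interval is 54.8-74.3%, about 19 points wide, and cannot lie inside a band of 68 − 61 = 7 points. The middle label can therefore be reached only by a single number.

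**Label probabilities.** Let X ~ Binomial(100, p). The rule says superior if X ≥ 69, non-inferior if 61 ≤ X ≤ 68, and inferior if X ≤ 60.

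| True sensitivity | Superior | Non-inferior | Inferior |
|---|---|---|---|
| 58% | 1.6% | 29.2% | 69.2% |
| 61% | 6.1% | 48.3% | 45.6% |
| 65% (benchmark) | 23.3% | 59.4% | 17.2% |
| 66.6% (centre's routine test) | 34.7% | 55.4% | 9.9% |

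At the benchmark, the wrong-label probability is 23.3% + 17.2% ≈ 40.5%. At a true 58%, below the inferiority cut-off, the assay is called non-inferior or superior 29.2% + 1.6% = 30.8% of the time.

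**What the data would say at the boundaries (exact 95% intervals).**

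- 60/100, labelled inferior: 49.7-69.7%.
- 61/100, labelled non-inferior: 50.7-70.6%.
- 69/100, labelled superior: 59.0-77.9%.

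One patient moves the verdict from inferior to non-inferior on almost the same interval. The interval behind a superior verdict can include 61%, 65% and 68%.

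**Precision.** The normal-approximation half-width at n = 100 is 1.96 × √(0.65 × 0.35 / 100) = 9.3 points. A half-width of 3.5 points, that of the band, needs n = 1.96² × 0.65 × 0.35 / 0.035² ≈ 713.

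**Other sample sizes, true sensitivity 65%.** Wrong-label probability:

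| n | 60 | 80 | 100 | 150 | 200 | 750 |
|---|---|---|---|---|---|---|
| Wrong label | 59.4% | 48.7% | 40.6% | 34.9% | 27.2% | 5.0% |

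**The same cut-offs applied to the exact 95% interval, n = 100.**

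- Lower limit above 68% first at 78/100 (68.6%).
- Lower limit above 61% first at 71/100 (61.1%).
- Upper limit below 61% last at 50/100 (60.2%).

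At a true 65%, P(X ≥ 78) = 0.3%, P(X ≤ 50) = 0.1% and P(X ≥ 71) = 12.4%.

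**The case against.** The strongest reply is that this is an exploratory, observational pilot that assigns no treatment. Where the routine test is already in use, EGFR decisions rest on it, and the raw sensitivity can be reported whatever label it receives. A separate analysis plan might add an interval. That lowers the stakes and excuses the lack of a power calculation. It does not excuse formal verdicts without error control, and an analysis plan that used intervals would have to override a rule stated twice in the protocol.

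The 40% figure is also tied to a truth exactly at the benchmark, and it adds two different errors; false superiority alone is 23.3%. Section 5 of the study rationale aside, the protocol expects that sequencing may be more sensitive (Section 4, study procedure), and at a true 75% the rule says superior 93% of the time. This stands as a limit on the figure. But the rule exists to tell such an assay from one that is merely equal, and there it fails.

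The extension clause is no rescue: no power is defined, so its trigger cannot be evaluated, and the error remains large at 150 or 200 patients.

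Finally, keeping 61% and 68% as bounds for an interval does not turn them into justified margins. That is fair, and it favours plain estimation. Nor is this the study's only comparison: it also sets rebiopsy rates against the previous year and the new assay against the routine test in EGFR-positive patients. Neither comparison repairs this rule.

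**Conclusion.** The concern holds, and the rule should be changed before it is used. Followed as written, it gives an assay identical to the benchmark a wrong label about 40% of the time: 23.3% falsely superior and 17.2% falsely inferior.

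This rests on 100 evaluable patients, a true sensitivity of exactly 65%, non-inferior being the correct label for an equal assay, and the inference that the observed proportion is what is compared with the cut-offs. Unevaluable samples, or restriction to EGFR-positive patients, would shrink the denominator and raise the error, as the figures for 80 and 60 patients show.

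**What to change.** Change the wording in Sections 2 and 5 in one of two ways.

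1. **Estimation.** Drop the three labels and report sensitivity with its exact two-sided 95% confidence interval, citing the meta-analysis only as context. This suits a pilot best and needs no margin.
2. **Interval-based rule.** Keep 61% and 68% as fixed benchmarks, with a sentence justifying them, and apply them to the exact two-sided 95% interval. Superior only if the lower limit exceeds 68% (at least 78/100); non-inferior only if it exceeds 61% (at least 71/100); inferior only if the upper limit is below 61% (at most 50/100); otherwise inconclusive. Recalculate the counts for the actual number evaluable.

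In either case, replace the not-applicable entries with the precision that 100 patients give, about ±9.3 points at 65%. Remove the extension sentence, or define its trigger and maximum size.

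Neither option needs extra patients. The cost of the second is that inconclusive becomes the likely result: at a true 65%, non-inferiority would be shown about 12% of the time, and at a true 75% superiority about 29%. For 80% power to show non-inferiority against 61% at a true 65% (one-sample normal approximation, one-sided 2.5%), n = [(1.96 × √(0.61 × 0.39) + 0.842 × √(0.65 × 0.35)) / 0.04]² ≈ 1,152 patients, far beyond this pilot.
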